## Testing Adaptive Interventions to Improve Physical Activity for Sedentary Women Study Protocol

### I. Purpose & Overview

The purpose of this study is to determine the most effective adaptive intervention combining four efficacious treatments (enhanced physical activity monitor, motivational text messaging, motivational personal calls, group meetings) to increase physical activity (step counts per day, minutes moderate/vigorous physical activity/week) and improve cardiovascular health (aerobic fitness, body composition) among sedentary women. This study with 312 women aged 18 to 70 will also assess treatment effects on intervention targets (benefits, barriers, self-efficacy, and social support). The four adaptive interventions compared in this study consist of an initial treatment component (*physical activity monitor* or *physical activity monitor+text messaging*) followed by an augmented treatment component (personal calls or group meetings) for those who do not respond to the initial treatment component. For ease of management, the research team will limit the augmented treatments to only two of the four factorial combinations of personal calls and group meetings. The research team will focus on personal calls only (least expensive) and group meetings (current standard) and accept inherent limitations. It is well-established that without intervention physical activity remains unchanged.

The combination of the two initial treatment components and the two augmented treatment components delivered to non-responders yields four adaptive interventions that will be evaluated in this study:

1. Start with enhanced *physical activity monitor*, augment with motivational personal calls for non-responders, and continue enhanced *physical activity monitor* for responders;
2. Start with enhanced *physical activity monitor*, augment with motivational group meetings for non-responders, and continue enhanced *physical activity monitor* for responders;
3. Start with enhanced *physical activity monitor+text messaging*, augment with motivational personal calls for non-responders and continue enhanced *physical activity monitor+text messaging* for responders; and
4. Start with enhanced *physical activity monitor+text messaging* augment with motivational group meetings for non-responders and continue enhanced *physical activity monitor+text messaging* for responders.

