Testing Adaptive Interventions to Improve Physical Activity for Sedentary Women

3/21/2018

NCT Number (not available yet)

Testing Adaptive Interventions to Improve Physical Activity for Sedentary Women

Statistical Analysis Plan

Under the direction of [name], SAS (v9.3) and R will be used for statistical analysis. Because multiple outcomes are being evaluated in the primary aim, a two-tailed .01 significance level will be used for the statistical tests of these hypotheses. Secondary and exploratory aims will employ a standard two-tailed significance level of .05 for all statistical tests. All analyses will be performed on an intent-to-treat basis. A one-way analysis of variance will be conducted to look for potential diffusion effects. If significant differences are found, the estimated mean levels of diffusion will be used as weights in the efficacy analyses and cost analysis. Hypothesis testing will address four study aims.

Aim 1. Aim 1 is to compare the two augmented treatments used for non-responders, personal calls and group meetings, in improving physical activity and cardiovascular health after 35 and 50 weeks.

Hypothesis: Group meetings will be more effective than personal calls in improving physical activity and cardiovascular health after 34 and 50 weeks, among non-responders to the initial treatment.

This hypothesis will be tested using a multilevel analysis with time nested within participant (i.e., non-responders only). The hypothesis of the study is that the non-responders who receive group meetings will demonstrate greater improvement in physical activity (self-report life-style and occupational physical activity: minutes of moderate/vigorous physical activity/weeks; device: number of steps/day, minutes of moderate/vigorous physical activity/ week) compared to those who receive personal calls.

Aim 2a. Aim 2a is to compare enhanced physical activity monitor with and without text messaging for improving the level of physical activity from baseline to 8 weeks. These analyses will parallel those used for Aim 1, but consider only two time points (baseline and 8 weeks) and include all participants.

Hypothesis: Participants who receive enhanced physical activity monitor+text messaging as compared to those who receive enhanced physical activity monitor alone will show greater improvement on physical activity at the end of 8 weeks.

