Aim 2b. Aim 2b is to compare the four adaptive interventions in improving physical activity and cardiovascular health from baseline to 8, 34, and 50 weeks. The analysis is parallel to that described in Aim 1, except that the participants are not assigned to treatment based on simple randomization. Instead, they are screened on the basis of response status, and, once it has been ascertained that they did not respond to the initial treatment, they are randomly assigned to a treatment condition. Due to this design, the contrasts used to estimate the efficacy of these effects are nonorthogonal. The weights associated with the four interventions are then scored as a 4 for non-responder subgroups and 2 for responder subgroups. This is because responder subgroups are used twice in the design matrix (e.g., subgroup A is used in adaptive interventions 1 and 2; Figures 2 and 3). The estimation of these models is then based on a weighted multilevel linear regression model that has terms for change over time, the initial treatment, the augmented treatment, the interaction between the two treatments, and the effects of baseline and time-varying characteristics. The critical effect in this model is the time-by-adaptive-intervention interaction term. The null hypothesis is that there will be no interaction effect at all, while the alternative hypothesis is that adaptive intervention 4 (enhanced physical activity monitor+text messaging [initial] and enhanced physical activity monitor+text messaging with group meetings [augmented for non-responders]) will produce the largest improvement rates.

Aim 3. Aim 3 will identify mediators and moderators of the initial and augmented treatments on physical activity and cardiovascular health. Using analytic models parallel to those for Aims 1 and 2, we will first test impact on intervention targets (benefits, barriers, self-efficacy, social support).

Hypothesis: The intervention targets (benefits, barriers, self-efficacy, and social support) will mediate the effect of the initial and augmented treatments on physical activity (8, 34, and 50 weeks) and cardiovascular health (34 and 50 weeks).

Research Question: Do characteristics of participants (prior physical activity, demographics, BMI, depression) and their environment (walkability, crime) moderate the effects of the initial and augmented treatments on physical activity and cardiovascular health?

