Although we will test the impact of each treatment on all potential intervention targets, we anticipate variation in impact by treatment (e.g., initial treatment is less likely to impact social support). For intervention targets that are significantly impacted by treatment condition, we will test whether they serve as mediators of intervention effects on physical activity and health status outcomes using methods described by MacKinnon. Moderation effects will be tested by adding moderator main effects and interactions of the moderators with condition and time. Significant moderator effects (i.e., significant moderator-by-time-by-treatment effects) will then be used to identify optimal decision rules for individual participants. The estimation of optimal decision rules will be achieved using a Q-Learning analysis, which is a modified regression analysis, adapted to address the SMART design. These optimal decision rules can then be cross-validated in future studies.

Aim 4. The cost-effectiveness analysis will be conducted from the societal perspective, including the program and participant costs. For the cost measurement, quantities of resources used and their associated prices will be collected for the program (either amounts paid or the value of the interventionist's time), and participant (i.e., the value of the participant's time to participate in the program). All costs will be valued in 2017 dollars. Program costs and participant costs will be calculated by summing their respective individual cost components, and these costs will be summed to calculate the total cost per participant.

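### Aim 3 tests mediation only for targets with a significant treatment effect, which inflates reported mediated effects on average when power is low and leaves other hypothesised mediators without an estimate

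*SAP*

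**What the plan says.** The Aim 3 hypothesis covers four targets and both treatment stages: "The intervention targets (benefits, barriers, self-efficacy, and social support) will mediate the effect of the initial and augmented treatments on physical activity". The bracket that follows lists Weeks 8, 34 and 50 for physical activity; cardiovascular health is given Weeks 34 and 50.

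The analysis has two steps. First, every target is tested for a treatment effect: "Although we will test the impact of each treatment on all potential intervention targets, we anticipate variation in impact by treatment". The example given is that the initial treatment is less likely to move social support, so some failures are expected. Second, mediation is taken up selectively: "For intervention targets that are significantly impacted by treatment condition, we will test whether they serve as mediators of intervention effects". The methods are cited by name only. No interval, no allowance for the selection and no mediation estimate for unselected targets is described. Protocol XII has the same text.

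Aim 3 is not labelled primary, so it appears to fall under this rule: "Secondary and exploratory aims will employ a standard two-tailed significance level of .05 for all statistical tests".

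**The concern.** A mediated effect is the product a × b, where a is the effect of treatment on the target and b is the effect of the target on the outcome given treatment. Keeping a target only when the estimate of a is significant retains the samples in which a happened to come out large. Estimating a × b from those samples carries the excess into the product.

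Aim 3 is meant to show which targets carry the treatment effect. If the a-path tests have low power, the mediators it reports will look stronger than they are on average. For a hypothesised mediator that fails, a reader cannot tell little mediation from imprecisely estimated mediation.

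Low power is plausible here, though not certain. Both contrasts compare active treatments that share content: both initial arms set step goals, and calls and group meetings both address barriers and benefits (Protocol V, VII, VIII). The augmented contrast also uses non-responders only.

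A separate problem is timing. Read literally, the hypothesis includes a path from the augmented treatments to 8-week activity.

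**Working it through.** **Inputs from the documents.** 312 women (Protocol I); 1:1 allocation at both randomizations (Protocol XI), so 156 per initial arm; two-sided .05, reading Aim 3 as secondary or exploratory.

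**Assumptions.** True effect d on a target, in SD units: 0.2 to 0.5. Non-response share: 50%, giving 312 × 0.5 / 2 = 78 per augmented arm, with a range of 30% to 60% (47 to 94 per arm). One unadjusted two-group comparison, no dropout. The plan states no power or effect size for Aim 3, so there is no figure to reproduce.

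**Formulas.** SE = √(2/n per arm); m = d/SE; c = 1.96. With Φ and φ the standard normal distribution and density:

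- pass rate P = Φ(m − c) + Φ(−c − m)
- average inflation given a pass = 1 + [φ(c − m) − φ(c + m)] / (P·m)

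**Initial treatment, d = 0.2.** SE = √(2/156) = 0.113; m = 1.766; P = 0.42, so 58% are skipped. Inflation = 1 + 0.391/(0.423 × 1.766) = 1.52.

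**Augmented treatment, d = 0.2.** SE = √(2/78) = 0.160; m = 1.249; P = 0.24, so 76% are skipped. Inflation = 1 + 0.308/(0.239 × 1.249) = 2.03.

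| True d | Initial (156 per arm): skipped, inflation | Augmented (78 per arm): skipped, inflation |
|---|---|---|
| 0.2 | 58%, 1.52 | 76%, 2.03 |
| 0.3 | 25%, 1.16 | 53%, 1.46 |
| 0.4 | 6%, 1.03 | 30%, 1.20 |
| 0.5 | 1%, 1.00 | 12%, 1.07 |

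**Does it carry over to a × b?** In a simulation with b = 0.3 (8,000 runs per case), the product without the filter averaged 0.99 to 1.00 of the truth. With the filter it averaged 1.51, 1.15 and 1.03 times the truth at d = 0.2, 0.3 and 0.4 with 156 per arm, and 2.02, 1.47 and 1.20 with 78 per arm. The b-path stayed unbiased, so the excess comes from a.

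**Sensitivity.**
- Non-response of 30% to 60%, augmented treatment: 2.51 to 1.87 times at d = 0.2; 1.78 to 1.36 times at d = 0.3.
- Half non-responders with an assumed 20% dropout (78 × 0.8 ≈ 62 per arm): 2.24 times at d = 0.2; 1.59 at d = 0.3.
- Adjustment for baseline with an assumed correlation of 0.6 multiplies the SE by √(1 − 0.36) = 0.8. Initial treatment: 1.29 times at d = 0.2, 1.05 at d = 0.3. Augmented: 1.68 and 1.24.
- If .01 applied instead, initial treatment: 1.78 times at d = 0.2, 1.28 at d = 0.3.

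**Timing.** The second randomization follows from responder status determined at Week 8 (Protocol IV, Decision Point 1; XI). Calls run in Weeks 11–34 (VII) and meetings start at Week 12 (VIII). Neither can affect 8-week activity. The targets are first re-measured at D2, Weeks 9–10, in the same questionnaire wave as self-reported activity (IV). Fitbit steps up to Week 8 come before that measurement.

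**The case against.** Several points on the other side stand.

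- A reader might infer that every reported mediated effect is 1.5 to 2 times too large. The documents do not support this. Inflation is an average over repeated trials, not a property of each estimate. That range arises only when the a-path test has about 25% to 44% power: d of about 0.14 to 0.20 at 156 per arm, or 0.20 to 0.29 at 78 per arm. The plan states neither d nor the non-response share.
- Nor does it follow that most modest mediators go unexamined. All four a-paths are tested, and at 0.3 SD only 25% of targets would miss the mediation step for the initial treatment.
- The filter does not create false mediators. An indirect effect needs a non-zero a, so as a test the filter costs power. The bias concerns the size of what is reported.
- Aim 3 uses models parallel to Aims 1 and 2, which are multilevel with repeated visits. The unadjusted SE is therefore probably pessimistic on that count, though dropout works the other way.
- It cannot be said that the planned interval ignores the selection, since no interval is specified.
- The 8-week augmented path may be compressed wording. Aim 1 confines the augmented comparison to about Weeks 34 and 50, and Aim 2a gives Week 8 to the initial treatment. A reader should not infer that such a model is planned, but the sentence as written includes it.
- It would be too strong to say that target and outcome can never be ordered at D2. The Actigraph is worn in the week after that visit and Fitbit data are continuous.

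None of this removes the filter, the average bias at low power, or the missing estimates for targets the hypothesis names.

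**Conclusion.** The concern holds in a conditional form. Selecting on significance and then estimating in the same data inflates Aim 3's mediated effects on average when power for the a-path is low, and targets that fail get no mediated-effect estimate. The inflation matters at about 0.2 SD and, for the augmented treatment, still at 0.3 SD. For the initial treatment it is small at 0.3 SD and negligible from 0.4 SD. These sizes rest on an assumed effect, an assumed 50% non-response and an unadjusted comparison; baseline adjustment lowers them and dropout raises them.

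The timing fault needs no assumption: mediation of the augmented treatments on 8-week activity is impossible.

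The change is worth making but is not critical, because Aim 3 appears to be secondary or exploratory.

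**What to change.** In SAP Aim 3 and Protocol XII:

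1. Delete the condition that a target must show a significant treatment effect before mediation is examined.
2. For all four pre-named targets, report a, b and a × b with bootstrap or equivalent intervals, and apply Holm across the four.
3. Limit the 8-week outcome to the initial treatment.
4. Describe results where target and outcome come from the same visit as associations.

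Lagged pairings (D2 target with 34-week outcome; D3 target with 50-week outcome) may be added, as sensitivity analyses only. The first spans a second randomization that only non-responders enter, so the SAP must state how that is handled; adjusting it for activity at D2 would also condition on a post-treatment variable. The second covers only the maintenance phase, after the added components stop.

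The cost is a wording change and the same models run for four targets, with no new data. The downside is that four intervals are reported, null ones included, and same-visit mediation is interpreted more weakly.

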  - Participants that are identified to have had issues with the monitors (e.g. they were not using them as instructed) will be asked to wear them for an additional week of wear time to re-evaluate their eligibility
  - Participants that are screened eligible based on their step count data will be contacted for scheduling their Baseline Interview

*Baseline Interview and Randomization (D1)*

- Because of changes related to COVID-19, participants will complete the D1 questionnaire online using a secure REDCap survey link
- D1 data collection will include the following:
  - Questionnaire completion:
    - Demographics (age, ethnicity, marital status, children, caregiver status, education, income/hardship, job, shift)
    - Neighborhood Environment Walkability Scale (NEWS)
      - 28 items assessing respondent's perceptions of characteristics in their neighborhood that are conducive to walking
    - Exercise Benefits/Barriers Scale (Revised for PA)
      - 43 items about statements that relate to positive/negative PA ideas
    - McAuley's Self-Efficacy for Overcoming Barriers to PA
      - 17 items reflecting beliefs in ability to continue to be physically active in the face of barriers
    - Social Support and Exercise (Revised for PA)
      - 13 items assessing scale of family and friend support
    - Outcome expectations
      - 11 items measuring expected change due to becoming more physically active
    - International Physical Activity Questionnaire (IPAQ) long-form
      - 27 items assessing days per week and hours/minutes per day of sitting, occupational, light, moderate, and vigorous leisure-time PA
    - Sedentary Behavior:
      - Time spent sitting participating in 9 sitting behaviors in past 7 days resulting in total minutes per week of sedentary behavior

- Emotional Distress-Depression Short Form 8b
  - 8 items measuring depressive symptoms over the past 7 days
- PROMIS Scale v 1.2
  - 10 items assessing general health, PA, emotional problems, and fatigue
- PROMIS Sleep Impact Short Form
  - 10 items, assessing past 7 days of sleep
- Participants will be asked to sign an Oath of Confidentiality agreement that notes that they will not discuss their experience with the physical activity program with anyone else in their workplace until after the participation in the study ends.
- Participants will be thanked for their time, and will schedule their program orientation appointment to occur within a target two-week window.

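### Aim 3 selects tailoring variables at an unadjusted .05 and fits decision rules to the same data with no internal validation, so with no true moderation a noise variable enters a rule in about 26% to 51% of analyses (one contrast, one outcome).

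*SAP*

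**What the plan says.** The moderation question in Aim 3 of the SAP begins: "Do characteristics of participants (prior physical activity, demographics, BMI, depression) and their environment (walkability, crime) moderate the effects". It covers both treatment stages and both outcome domains. That is six headings. Demographics is not broken down there, but the baseline interview (D1) in Protocol IV lists nine items: "Demographics (age, ethnicity, marital status, children, caregiver status, education, income/hardship, job, shift".

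The error level comes from the opening paragraph of the SAP: "Secondary and exploratory aims will employ a standard two-tailed significance level of .05 for all statistical tests". The same paragraph tightens the level for the primary aim only: "Because multiple outcomes are being evaluated in the primary aim, a two-tailed .01 significance level will be used".

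The route from test to rule is then stated in three sentences of Aim 3. Selection: "Significant moderator effects (i.e., significant moderator-by-time-by-treatment effects) will then be used to identify optimal decision rules for individual participants". Estimation: "The estimation of optimal decision rules will be achieved using a Q-Learning analysis, which is a modified regression analysis, adapted to address the SMART design". Validation: "These optimal decision rules can then be cross-validated in future studies". Protocol XII carries the same text.

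Neither document gives a multiplicity adjustment for Aim 3, a shortlist of tailoring variables, a hold-out sample, or any cross-validation, bootstrap or optimism correction within this trial.

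**The concern.** The plan describes a definite procedure, so this is more than missing detail. Significance at .05 decides which variables may enter a rule, and Q-learning then estimates the rule from the data that made those variables significant. Two problems follow.

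First, with several candidates, two treatment contrasts and several outcomes, some noise variables are expected to pass. The plan lowers the level in the primary aim because of multiple outcomes, but offers nothing comparable here, where there are more tests.

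Second, a variable chosen because its interaction was large in this sample has an overestimated interaction in this sample. Any value computed for the rule from the same data is therefore too high. Validation elsewhere does not correct that number, and a team deciding whether a rule merits a new trial would have no honest estimate to go on.

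At stake is whether a tailoring rule from Aim 3 can be told apart from noise. Aims 1 and 2 do not depend on it.

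**Working it through.** The documents give no power or error figure for Aim 3, so there is none to reproduce.

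**Inputs from the documents**
- Level per test: .05, two-tailed (SAP, opening paragraph).
- Candidates: 6 headings as listed (SAP, Aim 3). With demographics expanded by the D1 list: 9 + prior activity, BMI, depression, walkability, crime = 9 + 5 = 14.
- Contrasts: 2 (initial, augmented).
- Outcomes: Aim 3 names two domains only. The one explicit count is the six measures listed for Aim 4, used here as a proxy.
- Sample: 312 women (Protocol I).

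**Assumptions not in the documents**
- 50% non-response, so 312 × 0.5 = 156 women in the augmented-treatment contrast.
- Correlation between moderators of 0 to 0.5.
- For the second scenario below, an average difference of 0.3 SD between augmentations.

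**Step 1. Chance that noise enters a rule (one contrast, one outcome, no true moderation)**
For k independent tests, P = 1 − 0.95^k.
- k = 6: 1 − 0.95^6 = 0.265.
- k = 14: 1 − 0.95^14 = 0.512, with 14 × .05 = 0.7 false positives expected.
- k = 14 with correlation 0.5: 0.34 to 0.36 by simulation (2,000 trials per setting, n from 100 to 312).

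If a few moderators are real, noise can still join them. With 10 to 12 null candidates left, P = 1 − 0.95^10 = 0.40 to 1 − 0.95^12 = 0.46.

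**Step 2. Over the whole aim**
14 × 2 × 6 = 168 tests, and 168 × .05 = 8.4 false moderators expected if none is real. The expected count does not depend on the correlation between tests.

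**Step 3. What the rule then looks like**
In each simulated trial every moderator-by-treatment term was tested at .05. The significant ones went into a one-stage Q-learning regression, and the fitted rule was compared with giving everyone the better single option. A single change score stood in for the time interaction, and moderators were normal. Results are averages over trials in which a rule formed, in outcome SDs, for 14 independent candidates.

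| Scenario | n | In-sample gain of rule | True gain of rule |
|---|---|---|---|
| No moderation, no average difference | 156 | about 0.12 | 0 |
| No moderation, no average difference | 312 | about 0.08 | 0 |
| No moderation, one augmentation 0.3 SD better for all | 156 | about 0.07 | about −0.08 |

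With 14 candidates correlated 0.5 the null in-sample gain at n = 156 is still about 0.11, and with six candidates it is also about 0.11. The true loss in the 0.3 SD scenario is about 0.07 with six candidates or with correlation between the moderators. The assumptions therefore change how often a noise rule forms much more than how good it looks once formed.

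**The case against.** The strongest reply is that this is exploratory work, framed accordingly. Moderation is posed as a research question in a non-primary aim, and the plan itself points to later validation. An optimal decision rule is the usual technical name for what Q-learning estimates, not a claim of proven benefit. This stands, and it limits the severity. It does not supply error control or an honest value, and the plan nowhere labels the rules hypothesis-generating.

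The counts are also open to question. The SAP lists six headings. Fourteen comes from reading demographics through the D1 questionnaire, and items such as marital status, children and caregiver status are unlikely to be independent. This stands too, which is why the result is a range. The simulation is likewise simpler than the planned multilevel models and SMART-adapted Q-learning, and many of the real moderators are categorical. Its figures show the order of size only.

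A reader might infer more than the documents support:
- That half of all such analyses yield a rule made of noise. The 51% needs no true moderation, 14 separate candidates and near-independence, and applies to one contrast and one outcome.
- That a noise rule is always worse than one treatment for all. With no average difference it is neutral. The loss appears only if one component is truly better.
- That a 0.12 SD false gain goes with a 0.08 SD true loss. These come from different scenarios: when the loss is about 0.08 the apparent gain is about 0.07.
- That the rule is the trial's recommendation for individual women, or that an inflated gain will be published. The plan says neither. It says that rules will be identified and estimated.

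**Conclusion.** The concern holds as a flaw in a stated method, at the level of a cheap improvement. Followed as written, Aim 3 admits at least one noise moderator, for one contrast and one outcome, with probability of about 26% (six headings), about 35% (14 candidates correlated 0.5) or 51% (14 independent candidates), if nothing truly moderates. Across 14 candidates, two contrasts and six outcomes, about 8.4 false moderators are expected.

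With 156 non-responders, a rule built this way has an in-sample gain of about 0.12 SD against a true gain of 0. If one augmentation is 0.3 SD better for everyone, the rule appears about 0.07 SD better than giving it to all and is truly 0.07 to 0.08 SD worse. The 50% non-response, the 0.3 SD difference and the correlations are assumptions, and the six outcomes are borrowed from Aim 4.

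**What to change.** In Aim 3 of the SAP and in Protocol XII:

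1. Replace the .05 screen with a short list of tailoring variables named in advance, each with its coding, or with one penalised Q-learning fit on all candidates.
2. Estimate the value of the whole procedure, selection step included, by bootstrap or repeated cross-validation within this trial. Use the best of the four embedded adaptive interventions as comparator.
3. Report that optimism-corrected value with its interval, whatever its sign.
4. Label any rule hypothesis-generating until it has been validated in another study.

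A Bonferroni level alone would not be enough. At .05/14 = .0036 per test, 1 − (1 − .0036)^14 is about 0.049, so fewer noise variables would enter, but the value of a selected rule would still be estimated on the data that selected it.

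One could go further and claim a rule only if the corrected gain has a 95% interval above zero. For a non-primary question with no stated power that is a trade-off for the sponsor, and this point does not depend on it.

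The cost is more analysis code and revised wording, with no new participants, visits or data. The downside is fewer and more modest rules.
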